### **Participants Entering Escape Arm at Week 20, 24, 28, 32, 36, 40, 44, 48, 52, 56, 60, or 64**

Participants who do not maintain an acceptable response (have an EASI score <50% of baseline) at Week 20, 24, 28, 32, 36, 40, 44, 48, 52, 56, 60, or 64 in the Maintenance Period will be eligible for treatment in the Escape Arm and will receive 250 mg lebrikizumab Q2W through Week 68 in the Escape Arm in an open-label fashion. Participants not achieving an EASI-50 response at 2 consecutive visits after 8 weeks of treatment in the Escape Arm will be discontinued from the study.

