**Maintenance Period**

After completion of the Week 16 visit:

- Participants receiving 250 mg lebrikizumab Q2W
  - i. who achieve an IGA 0 or 1 and/or a  $\geq 75\%$  reduction in EASI score ( $\geq$ EASI-75) response at Week 16 will be randomly allocated to receive 250 mg lebrikizumab Q2W or 250 mg lebrikizumab Q4W, in a 1:1 fashion;
  - ii. who achieve neither an IGA 0 or 1 nor a  $< 75\%$  reduction in EASI score ( $<$ EASI-75) response at Week 16 will move to the Escape Arm.
- Participants receiving 250 mg lebrikizumab Q4W
  - i. who achieve an IGA 0 or 1 and/or an EASI-75 response ( $\geq$ EASI-75) at Week 16 will continue 250 mg lebrikizumab Q4W;
  - ii. who achieve neither an IGA 0 or 1 nor an EASI-75 response ( $<$ EASI-75) at Week 16 will move to the Escape Arm.
- Participants receiving placebo
  - i. who achieve an IGA 0 or 1 and/or an EASI-75 response ( $\geq$ EASI-75) at Week 16 will continue to receive placebo;
  - ii. who achieve neither an IGA 0 or 1 nor an EASI-75 response ( $<$ EASI-75) at Week 16 will move to the Escape Arm and will receive a loading dose of 500 mg lebrikizumab at Week 16 and Week 18.

Treatment regimen assignment will remain blinded during the Maintenance Period. Placebo injections will be utilized in order to maintain the blind and ensure that all participants receive the same number and frequency of injections regardless of treatment regimen assignment.

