**Escape Arm after Week 20:**

- Participants who do not maintain an EASI-50 response at Week 20, 24, 28, 32, 36, 40, 44, 48, 52, 56, 60 or 64 in the Maintenance Period will be assigned to an Escape Arm and receive lebrikizumab 250 mg Q2W as open-label treatment thorough Week 68.
- Participants not achieving an EASI-50 response at 2 consecutive visits in the Escape Arm after 8 weeks of treatment will be discontinued from the study.

During the Maintenance Period, participants will be instructed to self-administer study intervention. Administration by the participant or caregiver is recommended. If the participant or caregiver is not able to administer any dose throughout the study, study site staff may administer the injection.

- At Week 16, site personnel will instruct participants or their caregiver on the proper injection technique.
- At Week 16 and Week 18, participants or their caregiver will administer study intervention under site personnel supervision.
- Subsequent administration will be administered by participants or their caregiver at home.

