## **6.3. Measures to Minimize Bias: Randomization and Blinding**

### **Method of Treatment Assignment**

The randomization ratio and stratification factors are described in Section 4.1. The blinding scheme is described in Section 6.1.

Participants who achieve an IGA 0 or 1 and/or an EASI-75 response ( $\geq$ EASI-75) at Week 16 and do not use rescue therapy during the Induction Period are defined as responders. The responders originally assigned to lebrikizumab 250 mg Q2W will be re-randomized to either lebrikizumab 250 mg Q2W or lebrikizumab 250 mg Q4W. The responders originally assigned to 250 mg lebrikizumab Q4W or placebo will stay on their originally assigned treatment in the double-blind Maintenance Period at Visit 10 (Week 16).

Participants who achieve neither an IGA 0 or 1 nor an EASI-75 response ( $<$ EASI-75) at Week 16 and participants who require high-potency topical or systemic rescue treatment for AD during the Induction Period will be eligible for treatment in an Escape Arm. Participants who are eligible for the Escape Arm will receive blinded loading doses at Week 16 and Week 18, based on their prior treatment assignment, followed by 250 mg lebrikizumab Q2W through Week 68 in the Escape Arm in an open-label fashion.

All participants will be centrally assigned to randomized study intervention using an interactive web response system (IWRS). Before the study is initiated, the login information and directions for the IWRS will be provided to each site. Study intervention will be dispensed at the study

visits as summarized in the SoA (Section 1.3). Returned study intervention should not be re-dispensed to the participants.

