### 8.1. Efficacy and Health Outcome Assessments

#### 8.1.1. Efficacy Assessments

##### Eczema Area and Severity Index

The EASI assesses extent of disease at 4 body regions and measures 4 clinical signs: (1) erythema, (2) induration/papulation, (3) excoriation, and (4) lichenification each on a scale of 0 (clear) to 3 (severe). The EASI confers a maximum score of 72 (a higher score is more severe). The EASI evaluates 2 dimensions of AD: disease extent and clinical signs (Hanifin et al. 2001).

The EASI is assessed by the investigator and completed using a tablet device at the study visit.

Body surface area affected by AD will be derived from data collected as part of the EASI assessment.

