Participants will be stratified at randomization according to age (adolescent participants ≥ 12 to < 18 years vs ≥ 18 years) and disease severity (IGA 3 vs 4). Daily use of mid-potency TCS (low-potency TCS and/or topical calcineurin inhibitor [TCI] for sensitive areas) will be initiated at least 7 days prior to baseline in all participants (not allowed to be tapered or stopped during the Screening Period). Mid-potency TCS, low-potency TCS, and TCIs may be tapered or stopped after baseline, as needed, based on treatment response.

All study intervention injections during the Induction Period will be administered by site staff at the clinic.

Maintenance Period

After completion of the Week 16 visit:

- Participants receiving 250 mg lebrikizumab Q2W
 - i. who achieve an IGA score of 0 or 1 and/or a $\geq 75\%$ reduction in EASI score (\geq EASI-75) response at Week 16 will be randomly allocated to receive 250 mg lebrikizumab Q2W or 250 mg lebrikizumab Q4W, in a 1:1 fashion;
 - ii. who achieve neither an IGA score of 0 or 1 nor a $<75\%$ reduction in EASI score ($<$ EASI-75) response at Week 16 will move to the Escape Arm.
- Participants receiving 250 mg lebrikizumab Q4W
 - i. who achieve an IGA score of 0 or 1 and/or an EASI-75 response (\geq EASI-75) at Week 16 will continue 250 mg lebrikizumab Q4W;
 - ii. who achieve neither an IGA score of 0 or 1 nor an EASI-75 response ($<$ EASI-75) at Week 16 will move to the Escape Arm.
- Participants receiving placebo
 - i. who achieve an IGA score of 0 or 1 and/or an EASI-75 response (\geq EASI-75) at Week 16 will continue to receive placebo;
 - ii. who achieve neither an IGA score of 0 or 1 nor an EASI-75 response ($<$ EASI-75) at Week 16 will move to the Escape Arm and will receive a loading dose of 500 mg lebrikizumab at Week 16 and Week 18.

Treatment regimen assignment will remain blinded during the Maintenance Period. Placebo injections will be utilized in order to maintain the blind and ensure that all participants receive the same number and frequency of injections regardless of treatment regimen assignment.

Escape Arm

In the Escape Arm, participants will receive 250 mg lebrikizumab Q2W.

Escape Arm from Week 16:

- Participants who achieve neither an IGA score of 0 or 1 nor an EASI-75 response ($<$ EASI-75) at Week 16 will move to the Escape Arm.
- Participants who receive rescue treatment in the Induction Period will also be eligible to continue to the Escape Arm at Week 16.

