4.1.2. General Considerations for Analyses During Maintenance Period

Maintenance Period starts at the first injection of study intervention at Week 16 and ends on the date of Week 68 or the ETV (between Weeks 16 and 68) unless specified otherwise.

For the efficacy and health outcome analyses, baseline is defined as the last available value before the first injection in the Induction Period and, in most cases, will be the value recorded at Baseline Visit (Visit 2, Week 0).

Unless otherwise specified, efficacy and health outcome variables at Week 16 prior to entering the Maintenance Period will be presented for the visit-wise reports for the Maintenance Period.

Unless specified otherwise, for the safety analyses during the Maintenance Period, baseline is defined as the last available value before the first injection in the Maintenance Period. In most cases, this will be the measure recorded at Week 16. For TEAEs, baseline is the events ongoing just prior to the first injection of the study drug injection at Week 16.

For participants in the MPP and MSP who met escape criteria (EASI-50 non-response) and escaped to lebrikizumab 250 mg Q2W at Weeks 20, 24, 28, 32, 36, 40, 44, 48, 52, 56, 60 and 64, only data in the Maintenance Blinded Period (up to the time of escape) will be included in both efficacy and safety analyses.

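### Two Escape Arm rules are worded the wrong way round: the Week 20 to 64 trigger in Protocol 6.1, and the Week 16 rule for Q2W non-responders in Protocol 4.1 and SAP 1.2

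*Protocol*

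**What the plan says.** **Week 20 to 64 trigger.** Protocol 6.1, in the paragraph on escape at Weeks 20 to 64, reads: "Participants who do not maintain an acceptable response (have an EASI score <50% of baseline". Its next sentence removes people from the study on the opposite criterion: "Participants not achieving an EASI-50 response at 2 consecutive visits after 8 weeks of treatment in the Escape Arm". Protocol 4.1 gives the trigger as "Participants who do not maintain an EASI-50 response at Week 20" and the later listed visits. The Synopsis and Protocol 9.3 agree with 4.1, as do SAP 1.2, SAP 3 and SAP 4.1.2, the last of which refers to participants "who met escape criteria (EASI-50 non-response) and escaped to lebrikizumab 250 mg Q2W".

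**Week 16 rule, Q2W arm.** In the Maintenance Period list of Protocol 4.1, item i re-randomizes Q2W participants with IGA 0/1, EASI-75 or both. Item ii sends to escape those "who achieve neither an IGA 0 or 1 nor a" reduction of less than 75%. SAP 1.2 repeats this ("who achieve neither an IGA score of 0 or 1 nor a", then the same under-75% reduction). The matching Q4W and placebo items name failure to achieve EASI-75, as does Protocol 6.3: "Participants who achieve neither an IGA 0 or 1 nor an EASI-75 response".

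**Direction of the scale.** Protocol 8.1.1 states: "The EASI confers a maximum score of 72 (a higher score is more severe". SAP Appendix 1 derives EASI-50 as a change from baseline of -50% or lower, and loss of EASI-50 as a change above -50%.

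**The concern.** Both sentences say who changes treatment. The Protocol 6.1 text is the dosing section's only statement on entry to escape after Week 20. Read as written, it would take participants who are doing well off blinded treatment and leave relapsing ones in place, including placebo responders who have lost response and should be offered active drug.

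The analysis would be affected too. Under SAP 4.1.2 a participant's blinded Maintenance data stop at escape. Under the Maintenance primary estimand (SAP 1.1.1.2.1) escape is a treatment failure, with later values set to baseline. A participant moved in error while at 20% of baseline EASI would be analyzed as having had no improvement. The Maintenance results feed the Week 52 database lock that supports the initial Japanese submission (Protocol 9.5).

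**Working it through.** No stated figure is in dispute, so the check converts each rule to a common scale and compares it with the plan's own definitions.

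**Rule 1: Week 20 to 64 trigger**

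Inputs: EASI-50 means % change ≤ -50 and loss of EASI-50 means % change > -50 (SAP Appendix 1). % change = 100 × (score - baseline) / baseline.

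- Score / baseline < 0.50 ⇔ % change < -50 ⇒ EASI-50 is met.
- Loss of EASI-50 ⇔ % change > -50 ⇔ score / baseline > 0.50.

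Illustration with a baseline EASI of 30:

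| EASI | % of baseline | % change | EASI-50 response? | Escape by 6.1 parenthesis? | Escape by 4.1 rule? |
|---|---|---|---|---|---|
| 6 | 20 | -80 | yes | yes | no |
| 12 | 40 | -60 | yes | yes | no |
| 15 | 50 | -50 | yes | no | no |
| 15.1 | 50.3 | -49.7 | no | no | yes |
| 18 | 60 | -40 | no | no | yes |
| 30 | 100 | 0 | no | no | yes |

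The two wordings disagree at every score except exactly half of baseline, where neither fires.

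Scale: anyone with EASI-75 is at or below 25% of baseline and so already under the literal line. At the planning EASI-75 rates (Protocol 9.2):

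- Q2W: 120 × 0.58 = 69.6
- Q4W: 80 × 0.53 = 42.4
- Placebo: 80 × 0.20 = 16.0
- Sum: 128.0, and 128 / 280 = 45.7%

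This counts Week 16 scores that fit the wrong wording. It does not forecast misallocation.

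**Rule 2: Q2W arm at Week 16**

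| IGA 0/1 | EASI-75 | Item i (re-randomize) | Item ii, literal | Item ii, as in the Q4W and placebo lists |
|---|---|---|---|---|
| yes | yes | yes | no | no |
| yes | no | yes | no | no |
| no | yes | yes | **yes** | no |
| no | no | no | **no** | yes |

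Literally, the third row falls under both items and the fourth under neither. IGA 0/1 responders are never sent to escape by item ii.

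Scale, with n = 120, EASI-75 58% and IGA 0/1 38% (Protocol 9.2). The overlap of the two responses is not given, so it is bounded:

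| Assumption | EASI-75 without IGA 0/1 (third row) | Neither response (fourth row) |
|---|---|---|
| IGA 0/1 nested within EASI-75 | 120 × (0.58 - 0.38) = 24.0 | 120 × (1 - 0.58) = 50.4 |
| No overlap | 120 × 0.58 = 69.6 | 120 × (1 - 0.58 - 0.38) = 4.8 |

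**The case against.** The best defence is that no careful reader would follow either sentence literally. In Protocol 6.1 the words before the parenthesis already say that response has not been maintained. The Synopsis, Protocol 4.1 and 9.3, and the SAP all state the rule correctly, and no SAP population or derivation uses the reversed form. Item ii closes with the correct under-EASI-75 label and sits beside two correctly worded items. Protocol 4.1 (Escape Arm), 6.1 (Week 16 entry) and 6.3 assign Q2W participants with neither response to escape, so across the whole protocol nobody is left unassigned. Allocation is central through the IWRS, and the Maintenance Period is summarized descriptively with no between-group comparisons (Protocol 9.4.3.2, SAP 3).

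All of that stands, and it limits the weight of the point. The objections to the counts also have force. The 128 is simply the expected number of EASI-75 responders among all randomized participants, at a visit that is not a Week 20 to 64 trigger. The no-overlap bound is arithmetic only: someone entering with EASI of at least 16 who becomes clear or almost clear will usually have EASI-75 as well, so the nested figures are the more realistic.

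What does not follow is that the text can stay. Section 6.1 is where a site looks for dosing rules, and a plan that states an allocation threshold in both directions relies on the reader choosing the right one.

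**Conclusion.** Both rules are wrong as written. The Protocol 6.1 parenthesis reverses the escape trigger at every score except exactly 50% of baseline. Item ii for Q2W literally captures EASI-75 responders without IGA 0/1 (24 of 120 if the responses are nested, at most about 70) and misses those with neither response (about 50 if nested, about 5 with no overlap). These counts rest on the planning rates and an assumed overlap, and they measure how many scores fit the wording, not how many participants were misplaced.

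The intended rules are clear from the rest of the documents, and nothing shows that the IWRS or any site applied the stray text. Exposure is confined to the descriptive Maintenance Period. The Week 16 co-primary analysis, its alpha and its power do not depend on either sentence. This should be corrected because it is an operative treatment rule and the correction costs almost nothing.

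**What to change.** Correct the wording only and leave every threshold and the design as they are.

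- **Protocol 6.1, Weeks 20 to 64:** replace the parenthesis with *(less than 50% reduction from baseline in EASI, that is, an EASI score above 50% of baseline)*. This matches the SAP Appendix 1 derivation of loss of EASI-50 at every score.
- **Protocol 4.1, Q2W item ii:** use the Q4W and placebo wording, *neither IGA 0/1 nor EASI-75*. Item ii then becomes the exact complement of item i.
- **SAP 1.2, Q2W item ii:** make the same change.
- **IWRS:** check the programmed escape logic at Week 16 and at Weeks 20 to 64 against the corrected wording.

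The cost is three short edits in the next amendment and one specification check. No sample size, analysis or population definition changes.

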#### **6.1.1. Background Medication (Topical Treatment for AD)**

Background medication allowed during the study is described below.

All participants will be instructed to use a mid-potency TCS (hydrocortisone butyrate ointment 0.1%, or equivalent-potency TCS) for AD symptoms starting  $\geq 7$  days prior to the baseline visit (Day 1). Low-potency TCS (prednisolone cream 0.5% or equivalent-potency TCS) and/or TCI may be used for sensitive areas only (that is, face, neck, intertriginous, and genital areas)  $\geq 7$  days prior to the baseline visit (Day 1). Background medication is not allowed to be tapered or stopped until the baseline visit (Day 1).

Participants may taper or stop background medication use based on treatment response after baseline visit (Day 1). If AD lesions return or a participant experiences a flare, the background medication may be resumed at the participant and/or investigator's discretion.

Where possible, a mid-potency TCS (hydrocortisone butyrate ointment 0.1%) and a low-potency TCS (prednisolone cream 0.5%) will be provided by the sponsor for use in this study. If these specific TCS treatments are unavailable, an alternate, equivalent-potency TCS may be provided by the site.

Topical corticosteroid use, when the TCS is supplied by the sponsor, should be recorded via weight of returned tubes as indicated in the SoA (Section 1.3). The investigator must keep an accurate record of the number of tubes received, dispensed/used, and returned to the sponsor or designee. The sponsor or designee will provide forms to facilitate inventory control. All accountability forms and treatment logs must be retained in the investigator's permanent study

file, and these records must be available for inspection at any time by the sponsor, its designees, or by regulatory agencies.

Each container will be labeled as required per local country requirements.

## **6.2. Preparation/Handling/Storage/Accountability**

Investigational products will be supplied by Lilly or its representative, in accordance with current good manufacturing practices, and will be supplied with lot numbers, expiry dates, and certificates of analysis, as applicable.

The investigator or designee must confirm appropriate temperature conditions have been maintained during transit for all study intervention received and any discrepancies are reported and resolved before use of the study intervention.

Only participants enrolled in the study may receive study intervention and only authorized site staff may supply or administer study intervention. All study intervention must be stored in a secure, environmentally controlled, and monitored (manual or automated) area in accordance with the labeled storage conditions with access limited to the investigator and authorized site staff.

The investigator, institution, or the head of the medical institution (where applicable) is responsible for study intervention accountability, reconciliation, and record maintenance (that is, receipt, reconciliation, and final disposition records).

Follow storage and handling instructions stated on the IP label. Detailed instructions regarding preparation and handling of IPs will be provided by the Sponsor.

## **6.3. Measures to Minimize Bias: Randomization and Blinding**

### **Method of Treatment Assignment**

The randomization ratio and stratification factors are described in Section 4.1. The blinding scheme is described in Section 6.1.

Participants who achieve an IGA 0 or 1 and/or an EASI-75 response ( $\geq$ EASI-75) at Week 16 and do not use rescue therapy during the Induction Period are defined as responders. The responders originally assigned to lebrikizumab 250 mg Q2W will be re-randomized to either lebrikizumab 250 mg Q2W or lebrikizumab 250 mg Q4W. The responders originally assigned to 250 mg lebrikizumab Q4W or placebo will stay on their originally assigned treatment in the double-blind Maintenance Period at Visit 10 (Week 16).

Participants who achieve neither an IGA 0 or 1 nor an EASI-75 response ( $<$ EASI-75) at Week 16 and participants who require high-potency topical or systemic rescue treatment for AD during the Induction Period will be eligible for treatment in an Escape Arm. Participants who are eligible for the Escape Arm will receive blinded loading doses at Week 16 and Week 18, based on their prior treatment assignment, followed by 250 mg lebrikizumab Q2W through Week 68 in the Escape Arm in an open-label fashion.

All participants will be centrally assigned to randomized study intervention using an interactive web response system (IWRS). Before the study is initiated, the login information and directions for the IWRS will be provided to each site. Study intervention will be dispensed at the study

visits as summarized in the SoA (Section 1.3). Returned study intervention should not be re-dispensed to the participants.

### **Emergency Unblinding**

The IWRS will be programmed with blind-breaking instructions. In case of an emergency, the investigator has the sole responsibility for determining whether unblinding of a participants' intervention assignment is warranted. Participant safety must always be the first consideration in making such a determination. If a participant's intervention assignment is unblinded, the sponsor must be notified immediately after breaking the blind. The date and reason that the blind was broken must be recorded in the source documentation and eCRF, as applicable.

### **Unblinding and Participant Discontinuation**

If an investigator, site personnel performing assessments, or participant is unblinded, the participant must be discontinued from the study. For cases in which there are ethical reasons for the participant to continue the study, the investigator must obtain specific approval from a sponsor clinical research physician (CRP).

## **6.4. Study Intervention Compliance**

When participants are dosed at the site (first 16 weeks), they will receive study intervention directly from the investigator or designee, under medical supervision. The dose of study intervention and study participant identification will be confirmed at the time of dosing by a member of the study site staff other than the person administering the study intervention.

When participants self-administer study intervention(s) at home, compliance with study intervention will be assessed at each visit. Compliance will be assessed by direct questioning and checking the IP during the site visits and will be documented in the source documents and eCRF.

A record of the study intervention dispensed to and taken by each participant must be maintained and reconciled with study intervention and compliance records. Intervention start and stop dates, including dates for intervention delays, will also be recorded in the eCRF.

The date, time, and injection location of each dose administered will be recorded in the source documents and in the eCRF.

